	 Clinician acceptability assessed by ease of application and removal. Dressing wear time, dressing change frequency and conformability will be assessed. Scar quality measured by Patient and Observer Scar Assessment Scale (POSAS) score. 	

Study Protocol	Smith-Nephew
A prospective, study to evaluate the safety and performance of PICO 14 in the management of acute and chronic wounds	Number: PICO14.WND.PRO.2019.03
	Version: 2.0, 12SEP2021
	Page: 6 of 131

	Chronic Wounds and dehisced wound ONLY: To assess clinical performance and safety of the PICO 14 NPWT system within 28 days therapy period through: Incidence of infection. Dressing wear time, dressing change frequency and conformability will be assessed. Wound assessment: Appearance of the wound. Condition of peri-wound skin. Level of exudate. Wound pain. Size of wound (percentage reduction in area, depth, and volume). Patient tolerability assessed by level of pain and level of satisfaction. Clinician acceptability assessed by ease of application and removal.	
Other Objective(s):	No other objectives.	
Statistical Rationale:	Data extracted from a PICO sample device showed that the mean operating pressure was -80.2mmHg (SD=14.8). It is assumed that all the PICO 14 pumps will have a similar mean operating pressure. Based on these assumptions 55 subjects are required to achieve 80% power to detect equivalence within a 6mmHg margin, at the significance level of α = 0.025, using two one sided t-tests (TOST). It is expected that approximately 20% of the subjects may be lost to follow up by the end of the study and so to account for this 70 subjects will be recruited into the study.	
Sample Size:	The study will include 70 patients. There will be a minimum of 10 of each of the following wound type; venous leg ulcers, diabetes-related foot ulcers, pressure ulcers, dehisced surgical wounds and post-operative incisions.	
Number of Study Sites:	Up to ten.	
Targeted Global Regions	US, Canada, UK and Europe.	

Study Protocol	Smith-Nephew
A prospective, study to evaluate the safety and performance of PICO 14 in the management of acute and chronic wounds	Number: PICO14.WND.PRO.2019.03
	Version: 2.0, 12SEP2021
	Page: 7 of 131

Inclusion Criteria:

- The subject must provide written informed consent.
- Subjects eighteen (18) years of age or older.
- Willing and able to make all required study visits.
- Able to follow instructions.
- Subject is suitable to participate in the study in the opinion of the Investigator.

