The subjects will be described and summarised using the baseline demographic and medical variables which include but are not limited to age, gender, ethnicity, medical and medication history, diagnostic factors. Summary statistics will be given according to the nature of the variable; continuous or categorical.

11.4 EFFICACY ANALYSIS.

The study will assess and evaluate the efficacy of PICO 14 by establishing equivalence in the mean operating negative pressure over a period of 14 days with a pressure of -80.2 mmHg. The clinical efficacy of PICO 14 will be concluded if statistically significant equivalence (within an equivalence margin of ±6mmHg) is achieved. Secondary and exploratory outcomes will be evaluated to consolidate the primary outcome analysis.

The study is non-comparative and non-randomised, the impact of confounding on the measures of efficacy may be expected and will be evaluated through fitting appropriate models and adjusting for potential factors.

11.5 ANALYSIS OF PRIMARY ENDPOINT.

Delivery of -80mmHg negative pressure to the wound bed over the treatment period. This will be
measured by download of the built-in data chip from the PICO 14 devices to collect NPWT delivery
status.

The following hypotheses will be tested to establish equivalence of the PICO 14 integrated pump system compared to the literature value, with equivalence margin, δ_1 >0:

$$H_0: |\mu - \mu_0| \ge \delta_1$$

$$H_a$$
: $|\mu - \mu_0| < \delta_1$

In the stated hypotheses, μ represents the assumed mean operating pressure taken from data extracted from a PICO sample device (-80.2 mmHg) and μ_0 represents the mean PICO 14 pump operating pressure.

CONFIDENTIAL AND PROPRIETARY

Study Protocol—Device	Smith-Nephew
and performance of PICO 14 in the	Number: PICO14.WND.PRO.2019.03
	Version: 2.0, 12Sep2021
	Page: Page 96 of 131

The equivalence limit δ_1 = 6mmHg was chosen as a conservative non-clinically significant difference assuming that the difference is actually 0.

The average negative pressure across all subjects will be summarised as a continuous variable.

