The difference between the average negative pressure from baseline to treatment discontinuation and the assumed mean negative pressure (-80.2mmHg) will be calculated for each subject separately. This difference for closed incisions, dehisced surgical wounds and chronic wounds combined will be assessed using a two one-sided t-test at the alpha level of 0.025. The mean difference will be presented along with the associated 95% confidence interval and if the 95% confidence interval lies fully within the equivalence boundaries (-6; 6) then the null hypothesis is rejected and clinical equivalence will be confirmed.

As an additional analysis the above will be repeated separately for each wound indication.

 No occurrence of exudate leaks observed during the dressing wearing period resulting or not, in an unplanned dressing change.

Occurrence of exudate leaks in the opinion of the clinician will be recorded in the CRF. For non-occurrence of exudate leaks, a binary variable indicating presence of/absence of will be defined. For the combined group (closed surgical incisions, dehisced surgical wounds and chronic wounds) the frequency together with percentage of reported/identified outcome will be reported with a 95% CI. This will also be summarised separately for each wound indication.

Logistic models will be fitted and important associated factors adjusted for if there is adequate data.

Composite Clinical Success (CCS) defined as a binary variable (1/0) (1 if both of the following are true and 0 if either one is false):

- A. Nominal pressure is in the interval 80mmHg ± 6mmHg.
- B. No exudate leakage.

The CCS will be reported as a count and percentage with a 95% CI for the combined group and separately for each wound indication.

CONFIDENTIAL AND PROPRIETARY

Study Protocol—Device	Smith-Nephew
and performance of PICO 14 in the	Number: PICO14.WND.PRO.2019.03
	Version: 2.0, 12Sep2021
	Page: Page 97 of 131

11.6 ANALYSIS OF SECONDARY ENDPOINTS.

Closed Incision Only:

Clinical performance and safety of the PICO 14 NPWT system over a 14 day therapy and 30 day follow-up period to include:

- Scar quality measured by POSAS score at Day 14, and day 30.
- Incidence of Surgical Site Infection (SSI) and incidence of Surgical Site Complication (SSC) within 30 days of surgery [CDC criteria].
- Condition of peri-wound skin assessed through visual inspection at 7, 14 and 30 days.

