All safety analyses and summaries will be conducted using the Safety Population. Unless otherwise stated.

Extent of Exposure

The duration of treatment will be summarised by wound type and overall.

Adverse Events

The number of subjects reporting: adverse events, serious adverse events, adverse device effects, serious adverse device effects and unanticipated serious adverse device effects will be summarized. In addition, for each adverse

CONFIDENTIAL AND PROPRIETARY

Study Protocol—Device	Smith-Nephew
management of south and obvenie wounds	Number: PICO14.WND.PRO.2019.03
	Version: 2.0, 12Sep2021
	Page: Page 101 of 131

event, the following will be summarized: severity, the relationship to the investigational device, outcome and duration of the resolved adverse events and the duration of the adverse events at trial discontinuation.

Device deficiencies

The number of device deficiencies and the number of patients reporting a device deficiency will be summarised. The number of device defficiencies leading to a serious adverse device effect will also be summarised and they will be listed along with any corrective actions taken (if any).

11.9 INTERIM ANALYSES.

There is no interim analysis planned for this study.

11.10 SAMPLE SIZE JUSTIFICATION.

Data extracted from a PICO sample device showed that the mean operating pressure was -80.2 mmHg (SD=14.8). It is assumed that all the PICO 14 pumps will have a similar mean operating pressure. The following hypotheses will be tested to establish the clinical equivalence in mean operating pressure of PICO 14 integrated pump systems over a period of 14 days compared to the sample PICO pump mean pressure (-80.2mmHg) with equivalence margin, δ_1 >0:

$$H_0: |\mu - \mu_0| \ge \delta_1$$

$$H_a$$
: $|\mu - \mu_0| < \delta_1$

In the stated hypotheses, μ represents the assumed mean operating pressure of a PICO sample device (=-80.2mmHg, SD=14.8) and μ_0 represents the mean operating pressure of the study PICO 14 integrated pump systems. The equivalence δ_1 = 6mmHg was chosen as a conservative non-clinically significant difference for operating pressure assuming the difference is actually 0. The hypothesis will be tested by two one-sided t-test at the alpha level of 0.025. If the null hypothesis is rejected, clinical equivalence will be confirmed.

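### The 80% power claimed for 55 subjects is not supported: the source and type of the 14.8 mmHg SD are unstated, and even taken at face value it gives about 68% at 0.025 per side

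*Combined protocol and SAP*

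**What the plan says.** **Source of the SD.** Section 11.10 gives it as "Data extracted from a PICO sample device showed that the mean operating pressure was -80.2 mmHg (SD=14.8", and the synopsis says the same. The hypothesis text in 11.10 repeats that its reference parameter "represents the assumed mean operating pressure of a PICO sample device (=-80.2mmHg, SD=14.8", and describes the comparison as "compared to the sample PICO pump mean pressure (-80.2mmHg". Section 11.5 says that the reference "represents the assumed mean operating pressure taken from data extracted from a PICO sample device", but its lead-in sentence describes the aim as "to establish equivalence of the PICO 14 integrated pump system compared to the literature value". The same reference is therefore called sample-device data in one place and a literature value in another.

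**Link to the study pumps.** The only bridging assumption is "It is assumed that all the PICO 14 pumps will have a similar mean operating pressure". It concerns the mean. Nothing is assumed about variance.

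**What is tested.** Under 11.5 every subject contributes one value, a subtraction that the plan words as "average negative pressure from baseline to treatment discontinuation and the assumed mean negative pressure (-80.2mmHg) will be calculated for each subject separately". These differences, pooled over wound types, go into two one-sided t-tests at 0.025. Equivalence is declared if the 95% confidence interval lies inside (-6; 6).

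**The claim.** Section 11.10 states that at least 55 subjects give 80% power at 0.025 with SD 14.8 and a true difference of 0. It raises this to 70 for about 20% loss to follow-up.

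**The concern.** There are two separate gaps between the power statement and the test.

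1. *Which SD.* The test has one value per subject, averaged over the treatment period, so the SD that governs power is the spread of those averages between subjects. An SD attributed to a sample device could be the spread of readings over time in one pump, which is a different quantity. It could also be a between-device SD loosely described. The text does not let a reader tell which.

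2. *Which alpha.* Even if 14.8 is the right SD, 55 subjects do not give 80% power at the alpha the plan states.

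The stake is the credibility of the primary conclusion. If the study fails to show equivalence, nobody can tell from the plan whether that was a likely result of the sample size. If it succeeds, the design justification will still not survive a recalculation.

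**Working it through.** **Inputs (11.5 and 11.10).** SD 14.8 mmHg; margin 6 mmHg; true difference 0; 0.025 per one-sided test, confirmed by the 95% interval rule; power 80%; 20% loss; 70 recruited. Single arm, so a one-sample test.

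**Step 1: try to reproduce 55.** Normal approximation at true difference 0:

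power = 2 × Φ(6√n / SD − z) − 1

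With n = 55: 6 × 7.416 / 14.8 = 3.007.

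- 0.025 per side: 3.007 − 1.960 = 1.047; Φ = 0.852; power = 70.5%.
- 0.05 per side: 3.007 − 1.645 = 1.362; Φ = 0.913; power = 82.7%.

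Required n = (z + 1.2816)² × (14.8/6)², where (14.8/6)² = 6.084:

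- 0.025 per side: 3.2415² × 6.084 = 63.9, so 64.
- 0.05 per side: 2.9264² × 6.084 = 52.1, so 53.

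**Step 2: exact version.** Let τ = SD/√n, let t be the t quantile on n − 1 df, and let s = τ√(u/(n − 1)) with u chi-square on n − 1 df. Power is the integral over u of Φ((6 − ts)/τ) − Φ(−(6 − ts)/τ), taken as zero where ts ≥ 6.

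| Alpha per side | Power at 55 | Power at 56 | Power at 70 | n for 80% |
|---|---|---|---|---|
| 0.025 (stated) | 67.9% | 69.2% | 83.4% | 66 |
| 0.05 | 81.4% | 82.3% | 91.3% | 54 |

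The plan's 55 is not reproduced at the stated alpha. It is matched closely only at 0.05 per side. A single one-sided test at 0.025 gives 48 and a two-sample version gives more than 100 per arm, so neither explains 55.

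**Step 3: loss to follow-up.** 55/0.8 = 68.75, so 69, rounded up to 70. In the other direction, 70 × 0.8 = 56 evaluable. This step is sound. For 66 evaluable the same step gives 66/0.8 = 82.5, so 83 recruited.

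**Step 4: why the type of SD matters.** For a subject whose average rests on m effectively independent readings,

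variance of the average = between-subject variance + within-subject variance / m.

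If 14.8 is reading-to-reading spread, it belongs in the second term, which averaging shrinks. The first term is then not estimated anywhere in the documents. It would carry differences between wound types, seal quality, interruptions, and use of one or two pumps.

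**Step 5: size over a range.** The SDs below, other than 14.8, are assumptions. Exact power at 0.025 per side:

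| Between-subject SD (mmHg) | Power, 56 evaluable | Evaluable n for 80% |
|---|---|---|
| 10 | 98.6% | 32 |
| 12 | 91.4% | 44 |
| 14 | 76.6% | 60 |
| 14.8 | 69.2% | 66 |
| 16 | 57.5% | 77 |
| 18 | 37.7% | 97 |
| 20 | 20.1% | 119 |

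With 55 evaluable, 80% power needs a between-subject SD of at most about 13.5 mmHg; with 56, about 13.6.

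**The case against.** The strongest reply is that the documents never say 14.8 is a within-pump SD. The singular noun may be loose wording for several devices, and 11.5 calls the reference a literature value, which would more naturally come from a group of devices or patients. If 14.8 is reading-to-reading spread, averaging within each subject would tend to lower the relevant SD, and 55 could be more than enough. All of this stands. A reader might infer that the sponsor used the wrong SD, or that the study is underpowered because of where the SD came from. The documents support neither inference: they leave the source undefined, and the direction of any error is unknown.

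A reader might also infer that an unknown SD undermines the 6 mmHg margin. It does not. Sections 11.5 and 11.10 justify the margin as a clinically unimportant difference in the mean, and that judgement does not depend on pump-to-pump spread.

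Nor does testing against -80.2 while the endpoint names -80 matter here. A true difference of 0.2 mmHg moves power at 55 from 67.9% to 67.7%.

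The alpha shortfall is untouched by any of this. Documenting that 14.8 is a between-subject SD would settle the first gap and still leave about 68% power at 55.

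**Conclusion.** The stated 80% power with 55 subjects is not supported, on two counts of different strength.

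- **Firm.** On the plan's own inputs, 55 evaluable subjects give about 68% power at 0.025 per side, and the 56 expected from 70 recruited give about 69%. Reaching 80% takes 66 evaluable. This assumes normal data, a true difference of exactly 0 and a fixed reference of -80.2. That 0.05 per side was used in the calculation is an inference from the close match; the documents do not say so.
- **Open.** Whether 14.8 is the SD that the primary test needs cannot be settled from the text. The consequence is that the power is unknown, not that it is low. Over an assumed range of 10 to 20 mmHg it runs from about 99% to about 20% at 56 evaluable.

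This should be corrected, but it does not invalidate the primary analysis, whose decision rule in 11.5 is internally consistent.

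**What to change.** In 11.10 and the synopsis:

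1. State where the mean and SD came from, how many devices and readings they rest on, and whether the SD is within or between devices. Reconcile this with the description of the reference as a literature value in 11.5.
2. If the sponsor holds per-subject averaged pressures, use their between-subject SD. Section 16.3 mentions a pre-registration study, which is a place to look; the documents do not say whether it holds such data.
3. Replace the claim of 55 subjects for 80% power with the power that 70 recruited (56 evaluable) gives at 0.025 per side: about 69% at SD 14.8, with a table over an assumed range such as 10 to 20 mmHg. Keep the alpha in the calculation the same as the alpha and 95% interval in 11.5.

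The cost is a wording change and a rerun of the calculation; the separate SAP is still to be finalised before database lock and can carry the same text. The downside is that the stated power may become less favourable. No change to enrolment is required. If the sponsor wants 80% at SD 14.8, that is a separate decision and means 66 evaluable, or 83 recruited.

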Based on data and assumptions used for sample size estimation (mean=-80.2mmHg, SD=14.8), a minimum of 55 subjects are required to achieve 80% power to detect equivalence at the significance level of α = 0.025 within

CONFIDENTIAL AND PROPRIETARY

Study Protocol—Device	Smith-Nephew
and performance of PICO 14 in the	Number: PICO14.WND.PRO.2019.03
	Version: 2.0, 12Sep2021
	Page: Page 102 of 131

6mmHg using a two one-sided t-test (TOST) approach. Drawing from past experience, it is expected that approximately 20% of the subjects may be lost to follow up by the end of the study and therefore to account for this N=70 subjects will be recruited into this study. This will allow for a minimum of 10 subjects with each of the following indications to be recruited: Chronic open wounds (pressure ulcers, venous leg ulcers and diabetes-related foot ulcers), dehisced surgical wounds and closed surgical incisions (post-operative incisions following hip or knee arthroplasty).

The sample size was estimated using SAS V9.4.

12. ADVERSE EVENTS AND DEVICE DEFICIENCIES.

12.1 DEFINITIONS.

The categories of adverse events are shown in table 12.1-1. The definitions for each of these categories are given in the subsequent sections. Table

12.1-1: Categories of Adverse Event

	NOT DEVICE-RELATED	DEVICE- OR PROCEDURE- RELATED	
Non-Serious	Adverse Event (AE)	Adverse Device Effect (ADE)	
Serious	Serious Adverse Event (SAE)	Serious Adverse Device Effect (SADE) (See 12.1.3)	
		Anticipated	Unanticipated
		Anticipated Serious Adverse Device Effect (ASADE)	Unanticipated Serious Adverse Device Effect (USADE)

CONFIDENTIAL AND PROPRIETARY

Study Protocol—Device	Smith-Nephew
and performance of PICO 14 in the	Number: PICO14.WND.PRO.2019.03
	Version: 2.0, 12Sep2021
	Page: Page 103 of 131

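### 55 subjects give about 68% power, not the stated 80%, for the planned equivalence test at 0.025 per side; 80% needs 66 evaluable subjects

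*Combined protocol and SAP*

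**What the plan says.** The sample size appears twice with the same figures. Section 11.10 says that "a minimum of 55 subjects are required to achieve 80% power to detect equivalence at the significance level of α = 0.025 within" 6 mmHg by the TOST approach. The Statistical Rationale row of the synopsis says that "55 subjects are required to achieve 80% power to detect equivalence within a 6mmHg margin, at the significance level of α = 0.025". Both then allow for about 20% loss to follow-up and recruit 70.

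The test is described consistently. Section 11.10: "The hypothesis will be tested by two one-sided t-test at the alpha level of 0.025". Section 11.5 says the difference for all wound types "combined will be assessed using a two one-sided t-test at the alpha level of 0.025", and gives the decision rule: "if the 95% confidence interval lies fully within the equivalence boundaries (-6; 6) then the null hypothesis is rejected". Section 11.4 concludes clinical efficacy if equivalence is shown "within an equivalence margin of ±6mmHg". The planning values are also in 11.10: "Based on data and assumptions used for sample size estimation (mean=-80.2mmHg, SD=14.8"), with the margin set "for operating pressure assuming the difference is actually 0".

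**The concern.** Requiring a 95% confidence interval to lie inside the margins is the same as running each one-sided test at 0.025. The alpha and the interval rule therefore agree with each other, but the sample size does not agree with them: 55 is too small for 80% power with this SD and margin, and is about what the less strict 0.05-per-side test would need.

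Two things are at stake. First, section 11.4 rests the efficacy conclusion on this one test, and section 5.5 puts the study to use in continuing CE marking. On the planning assumptions, a device exactly on target would miss equivalence about one time in three, not one in five. Second, because 55 fits a 90% interval rule, a later move from 95% to 90% could be presented as a correction after the result is known.

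**Working it through.** **Inputs, all from the protocol**
- Design: one average pressure per subject, compared with the fixed value -80.2 mmHg (11.5)
- SD σ = 14.8 mmHg (11.10)
- Margin δ = 6 mmHg (11.4, 11.5, 11.10)
- True difference 0 (11.10)
- α = 0.025 for each one-sided test (11.5, 11.10), confirmed by the 95% interval rule (11.5)
- Stated result: n = 55, power 80%

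**Method.** Equivalence is declared when |mean difference| + t(1−α, n−1) × s/√n < δ. Power was obtained exactly by integrating the probability of this event over the chi-square distribution of the sample variance. With a true difference of 0 and these inputs, this agrees to four decimals with 2 × P(T > t(1−α, n−1)) − 1, where T is noncentral t with n−1 degrees of freedom and noncentrality δ√n/σ.

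**At the stated n = 55, α = 0.025 per side**
- Standard error: 14.8/√55 = 1.996
- Noncentrality: 6/1.996 = 3.007
- Critical value: t(0.975, 54) = 2.005
- P(T > 2.005) = 0.8396
- Power = 2 × 0.8396 − 1 = 0.679

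A simulation of 200,000 trials also gave 0.679. The normal approximation gives 2 × Φ(3.007 − 1.960) − 1 = 2 × 0.8524 − 1 = 0.705, so the choice of approximation does not rescue 80%.

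**Power by number evaluable**

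| n | 0.025 per side (95% interval) | 0.05 per side (90% interval) |
|---|---|---|
| 54 | 66.5% | 80.5% |
| 55 | 67.9% | 81.4% |
| 56 | 69.2% | 82.3% |
| 65 | 79.2% | 88.8% |
| 66 | 80.1% | 89.3% |
| 70 | 83.4% | 91.3% |

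**Sample size for 80%.** With β = 0.20 split over the two sides, the normal approximation is n = (z(1−α) + z(0.90))² × (σ/δ)²:
- α = 0.025: (1.960 + 1.2816)² × (14.8/6)² = 63.9, so 64; exact with t, 66
- α = 0.05: (1.645 + 1.2816)² × (14.8/6)² = 52.1, so 53; exact with t, 54

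**Can 55 be reproduced another way?**
- 0.05 per side: 54 needed, and 55 gives 81.4%. This is the only close match.
- 0.025 split across both tests (0.0125 per side): 51.3% power at n = 55, which is further away.
- β not halved, α = 0.025: 48 (normal) or 50 (t).
- β not halved, α = 0.0125: 58 (normal) or 61 (t).
- Two-sample form: 96 per arm.
- True difference 0.2 mmHg, α = 0.025: 67 needed.

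**Loss to follow-up.** 55/0.8 = 68.75, so 69, consistent with recruiting 70. After 20% loss, 70 × 0.8 = 56 evaluable, with 69.2% power. Reaching 66 of 70 allows the loss of only 4 subjects, 4/70 = 5.7%.

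**The case against.** The arithmetic is not in dispute; the objections are to what is drawn from it.

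- **Origin of 55.** Section 11.10 names only SAS V9.4 and shows no calculation, and at 0.05 per side the exact minimum is 54, not 55. That the sample size was worked out for a 90% interval is therefore an inference. This stands, but the error does not depend on where 55 came from.
- **The SD.** The 14.8 came from a sample device, while 11.5 analyses one average per subject, and the protocol does not show that these vary alike. At n = 55 and 0.025 per side, power is 90.7% at SD 12, 80.7% at SD 13.4 and about 56% at SD 16. The trial's real power is therefore unknown. This also stands, but the protocol derives its 80% from 14.8, and from 14.8 it does not follow.
- **Evaluable number.** Someone lost to follow-up may still supply pressure data: the value comes from the returned pump, the full analysis set needs only one post-baseline visit (11.2), and data up to withdrawal may be used (7.8.4). More than 56 may thus be evaluable. Lost pumps (7.8.1) and the per-protocol analysis work the other way. The 56 is the protocol's own planning scenario, not a forecast.
- **Direction of harm.** The test and interval rule agree and hold 0.025 per side, so false claims of equivalence are not inflated. The cost is a greater chance of an inconclusive primary result. That is correct, but it leaves the power statement for the primary hypothesis wrong.

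**Conclusion.** The concern holds. On the protocol's own assumptions (SD 14.8 between subjects' averages, normal data, true difference 0, margin ±6 mmHg, 0.025 per side), 55 subjects give 67.9% power. This is 12.1 percentage points below the stated 80%. Type II error is 32.1%, not 20%, and 80% needs 66 evaluable subjects, 11 more than stated. The planned loss allowance does not close the gap, and even all 70 evaluable would give only 83.4%. The conclusion is that the stated power does not follow from the stated inputs. It is not an estimate of what the trial will achieve, which depends on the true between-subject SD and on how many pumps yield data.

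**What to change.** This must be corrected. In the synopsis (Statistical Rationale) and section 11.10, and in the SAP, state that 55–56 evaluable subjects give about 68–69% power for TOST at 0.025 per side with the 95% interval rule, and that 80% needs 66 evaluable. This is a change of wording and needs no added enrolment; its cost is a less favourable power statement.

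If the sponsor actually meant 0.05 per side, the alpha and the interval level (90% in place of 95%) must be changed together in the synopsis, 11.5 and 11.10, with a justification, and declared before any pressure data are seen. Changing only one of them would leave the plan inconsistent.

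If the sponsor prefers to keep both 80% power and the 95% rule under the planned 20% loss, the recruitment target would be 66/0.8 = 82.5, so 83 rather than 70. That is a choice for the sponsor and not a condition of correcting the statement.
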